6.8. Multiple Comparisons/Multiplicity

No adjustments for multiplicity are planned.

7. STUDY SUBJECTS

7.1. Subject Disposition

The disposition of subjects in the study will be tabulated by randomized treatment group and all subjects. Table 2 shows the number of subjects who are screen failures and the number of subjects that met each inclusion/exclusion criterion. Table 3 summarizes the ITT and mITT population eligibilities by randomized treatment group and reasons excluded and Table 4 summarizes the safety, Evaluable and PP analysis population eligibilities by actual treatment group and reasons excluded. Subjects will be included in the count for a particular reason for Exclusion if they met that criterion. As subjects may meet more than one criterion for exclusion, the "Excluded from..." counts may be less than the sum of the individual reason counts. A listing of the subjects excluded from each of the analysis populations and the reasons for exclusion will be provided (Listing 4). The number of enrolled subjects in the study completing study milestones will be tabulated separately by randomized treatment group. Table 5 shows the total number of subjects enrolled, randomized, treated, complying with treatment, completing Visits 2, and 3, and completing Visits 2 and 3 and in the PP population by randomized treatment group. A listing of subjects who completed the study, terminated early from study, or discontinued treatment and the reason for early termination or treatment discontinuation is included in Listing 1.

Figure 1 is a flowchart showing the disposition of study subjects in the primary efficacy analysis, adapted from the CONSORT statement. It shows the number of subjects eligible, enrolled and randomized, lost to follow-up, and analyzed for the primary efficacy analysis, overall and by treatment group.

7.2. Protocol Deviations

A summary of subject-specific protocol deviations will be presented by the deviation category, the type of deviation, and randomized treatment group for all enrolled subjects (**Table 6**). All subject-specific protocol deviations and non-subject-specific protocol deviations will be included in Appendix III as data listings (**Listings 2** and **3**, respectively).

8. EFFICACY EVALUATION

All efficacy variables will be listed by subject and summarized by analysis population and treatment group. Continuous efficacy variables will use some or all of the following: N, Mean, Standard Deviation, Median, Minimum and Maximum, whereas Number and Percent will summarize categorical efficacy variables. Confidence intervals for binomial proportions and difference in binomial proportions will be computed using the Wilson confidence limits.

8.1. Primary Efficacy Analysis

The primary efficacy endpoint is the proportion of subjects with clinical cure in each study arm at Visit 2 (Day 8-15), TOC.

A test of hypothesis comparing the proportion of subjects who achieve clinical cure at the Test of Cure Visit, Visit 2 (Day 8-15), will be conducted in the mITT population using the randomized treatment, and repeated as a secondary analysis using the actual treatment received in the PP population and the Evaluable analysis population, and using the randomized treatment in the Intent-to-Treat population. The null hypothesis for each comparison is that there is no difference in proportions of clinical cure between treatment groups, with a two-sided alternative that considers the possibility of a difference in either direction. Fisher's exact test at the 5% two-sided level of significance will be used without adjustment for multiplicity. The number of subjects, the proportion of subjects who achieved clinical cure (clinical cure will be presented for each analysis population and treatment group. In addition, the difference in proportions between the 5% Monolaurin Vaginal Gel arm and the Placebo gel arm and 95% Wilson confidence intervals will be presented. See **Table 29**. See Section 6.1 for pseudocode to fit the above analyses.

A subject listing of individual Amsel criteria will be provided in Listing 22. A summary of Amsel criteria is provided for subjects by visit and site in Table 33. The number of Amsel criteria present (0,1,2,3,4), pH (> 4.5, \leq 4.5), Clue cells (\geq 20%, < 20%), Amine ("whiff") test on KOH wet mount (Positive, Negative), and discharge (yes/no) will be summarized. A summary of Amsel criteria is provided for subjects by visit and treatment group for each analysis population in Tables 34-37. Individual efficacy response data is presented in Listing 10. Reasons for clinical failure are provided in Listing 24.

8.2. Secondary Efficacy Analyses

Secondary efficacy analyses will be performed in the mITT, ITT, Evaluable and PP populations. The mITT and ITT populations will be summarized by randomized treatment and the Evaluable and PP populations will be summarized by actual treatment received.

Table 30 presents the proportion of subjects with clinical cure in each treatment group at Visit 3 (Day 22-31). The number of subjects, the proportion of subjects who achieved clinical cure (clinical cure rate), and the 95% Wilson confidence interval for the proportion of subjects achieving clinical cure will be presented for each analysis population and treatment group. In addition, the difference in proportions between the 5% Monolaurin Vaginal Gel arm and the Placebo gel arm and 95% Wilson confidence intervals will be presented.

Tables 31 and 32 present the proportion of subjects with therapeutic cure in each treatment group at Test of Cure Visit, Visit 2 (Day 8-15) and at Visit 3 (Day 22-31), respectively. The number of subjects, the proportion of subjects who achieved therapeutic cure (therapeutic cure rate), and the 95% Wilson confidence interval for the proportion of subjects achieving therapeutic cure will be presented for each analysis population, treatment group, and study visit. In addition, the difference in proportions between the 5% Monolaurin Vaginal Gel arm and the Placebo gel arm and 95% Wilson confidence intervals will be presented.

Tables 38-41 presents the number and proportion of subjects with Nugent scores falling in negative BV (3 or less), intermediate (4-6), and BV (7-10) range by analysis population, study visit, and site. The 95% Wilson confidence intervals for the proportion of subjects falling in each category will also be presented. **Tables 42-43** presents the proportion of subjects with Nugent score of 3 or less (negative for BV), 4-6 (intermediate), and 7-10 (positive for BV) in each treatment group at Visit 1, at Visit 2 (Day 8-15) and at Visit 3 (Day 22-31). The number and proportion of subjects with Nugent scores falling in negative, intermediate, and BV range is presented by analysis population, study visit, and treatment group. The 95% Wilson confidence intervals will also be presented. Mean Nugent scores will also be presented by analysis population, study visit, and treatment group in **Table 44.** A subject listing of Nugent scores and bacterial morphotypes will be presented in **Listing 23**. Raw Nugent scores are displayed graphically by visit, treatment group, and analysis population in **Figures 2-5**. Categorical and Continuous Nugent Score characteristics are presented by study visit, clinical cure status, and treatment group for subjects in the ITT population in **Tables 45 and 46**. See Section 6.1 for pseudocode to use in calculating the 95% CIs.

8.3. Exploratory Efficacy Analyses

Exploratory efficacy analyses will be performed in the mITT, ITT, Evaluable and PP populations. The mITT and ITT populations will be summarized by randomized treatment and the Evaluable and PP populations will be summarized by actual treatment received.

The first exploratory efficacy endpoint is the proportion of subjects with clinical cure in each treatment group by subgroup (first time or recurrent infection) at the Test of Cure Visit, Visit 2 (Day 8-15) and at Visit 3 (Day 22-31). The number of subjects, the proportion of subjects who achieved clinical cure (clinical cure rate), and the 95% Wilson confidence interval for the proportion of subjects achieving clinical cure will be presented for each analysis population, treatment group, and infection type (first time or recurrent). In addition, the difference in proportions between the 5% Monolaurin Vaginal Gel arm and the Placebo gel arm and 95% Wilson confidence intervals will be presented. See **Tables 47-50**. A listing of subjects BV infection status (first time or recurrent) will be provided in **Listing 25**. See Section 6.1 for pseudocode to use in calculating the 95% CIs.

The second exploratory efficacy endpoint is the proportion of subjects with therapeutic cure in each study arm by subgroup (first time or recurrent infection) at the Test of Cure Visit, Visit 2 (Day 8-15) and at Visit 3 (Day 22-31). The number of subjects, the proportion of subjects who achieved therapeutic cure (therapeutic cure rate), and the 95% Wilson confidence interval for the proportion of subjects achieving therapeutic cure will be presented for each analysis population, treatment group, and infection type (first time or recurrent). In addition, the difference in proportions between the 5% Monolaurin Vaginal Gel arm and the Placebo gel arm and 95% Wilson confidence intervals will be presented. See **Tables 51-54**.

The third exploratory efficacy endpoint is the mean count of *Lactobacillus spp.*, *Gardnerella spp.*, and *Mobiluncus spp.*, respectively, in each treatment group at Visit 1, at Visit 2 (Day 8-15) and at Visit 3 (Day 22-31). Mean count and standard deviation of each specimen type will be presented by study visit, analysis population, and treatment group. Additionally, mean change from baseline and corresponding standard deviation will be presented for Visit 2 and Visit 3. See **Tables 57-60**.

The fourth exploratory efficacy endpoint is the mean fungal colony count of *Candida spp*. in vaginal secretions in each study arm at baseline, at Visit 2 (Day 8-15) and at Visit 3 (Day 22-31). Mean count and standard deviation will be presented by study visit, analysis population, and treatment group for subjects with *Candida spp*. identified by either positive culture counts or presence of budding yeast organisms at screening. Additionally, mean change from baseline and corresponding standard deviation will be presented for Visit 2 and Visit 3. See **Table 61**.

9. SAFETY EVALUATION

9.1. Demographic and Other Baseline Characteristics

Ethnicity and race will be summarized by site in **Table 7** and by randomized treatment group in **Table 9**. Ethnicity is categorized as Hispanic or Latino, or Not Hispanic or Latino. Race is categorized as American Indian or Alaska Native, Asian, Native Hawaiian or Other Pacific Islander, Black or African American, White, Multi-Racial or Unknown In accordance with NIH reporting policy. Subjects may self-designate as belonging to more than one race (Multi-Racial) or may refuse to identify a race (Unknown), the latter reflected in the Case Report Form (CRF) as "No" to each racial option. Age and episodes of BV (including current episode) in the previous 12 months (from the sexual history questionnaire) will be summarized by site in **Table 8** and by randomized treatment in **Table 10**.

Baseline sexual history will be presented by site in **Table 11** and by randomized treatment group in **Table 12** for all enrolled subjects.

Baseline clinical assessment of BV will be presented by sign/symptom, maximum severity, and site for subjects in the Safety population in **Table 13**. Baseline clinical assessment of BV will be presented by sign/symptom, maximum severity, and actual treatment group for subjects in the Safety population in **Table 14**.

Individual subject listings will be presented for all demographics (Listing 5); sexual history (Listings 7-8).

9.1.1. Concurrent Illnesses and Medical Conditions

All current illnesses and past pre-existing medical conditions will be MedDRA[®] coded using MedDRA[®] dictionary version 20.1 or higher. Summaries of subjects' pre-existing medical conditions will be presented by randomized treatment group overall and by each site (**Tables 15-18**).

Individual subject listings will be presented for all medical conditions (Listing 6).

9.2. Measurements of Treatment Compliance

All subjects are to receive a total of six doses of study product (twice daily for three consecutive days). The first dose is administered in clinic and the remaining 5 doses will be administered by the subject at home. Subjects record the timing of all remaining doses on a memory aid, which is reviewed with clinic staff at Visit 2. Compliance is assessed by the study coordinator's count of used/unused applicators in each returned subject kit. If a kit is not returned, compliance will be

assessed by the subject's self-report on the memory aid. If an incomplete kit is returned, the subject's self-report will be used in conjunction with the count of used/unused applicators to determine subject compliance. In addition to the count of used/unused applicators, the timing of dosing will be considered. Subjects are instructed to administer study product twice daily (morning and evening) with at least 8 hours between doses. If the subject received her first dose after 3 pm, she will be instructed to administer the next dose the following morning. A subject is compliant if she uses at least 5 of 6 doses and they were administered within 72 hours from the first dose, at least 8 hours apart, and if no more than 2 doses in a 24 hour period are taken.

If a subject is found to have a positive test for HIV, chlamydia or gonorrhea or a Grade 3 laboratory abnormality from Visit 1, she will be notified of the results, withdrawn from receiving further study product, but will be followed for safety and efficacy. All subjects who were randomized will be followed for safety and efficacy. If any subject experiences a severe AE related to the study product, further doses will be discontinued.

The dates of first treatment are presented for subjects in the Safety population by site in **Table 19** and actual treatment group in **Table 20**. The number of subjects not compliant with study treatment will be presented by treatment group as part of the subject disposition table (**Table 5**). The number of doses administered as scheduled and out of window is summarized for subjects in the Safety population by site in **Table 21** and by actual treatment in **Table 23**.

Administration schedule is categorized as either "as scheduled" or "out of window." As scheduled is defined as twice daily (morning and evening) with at least 8 hours between doses as reported on the memory aid. **Tables 22 and 24** show the number and percentage of subjects who received the dose as scheduled, received the dose out of window, or missed the dose, for each of the 6 doses, by site and actual treatment group, respectively for subjects in the Safety population.

Table 25 displays product administration position by site and number of doses administered and Table 27 displays product administration position by actual treatment group and number of doses administered for the subjects in the Safety population. Product administration position is categorized as either "Recumbent" or "Not Recumbent." A subject contributes to the "Recumbent" rows if they administer each of the specified number of doses in the recumbent position. If a subject was not recumbent for at least one of the specified number of doses or is missing product administration position, they will appear in the "Not Recumbent" rows. Tables 26 and 28 show the number and percentage of subjects who received the dose and remained in the recumbent position, received the dose and did not remain in the recumbent position, or did not enter the position they were in for the dose, for each of the 6 doses, by site and actual treatment group, respectively for subjects in the Safety population.

Individual subject listings of treatment compliance assessment will be presented (Listing 9).

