10. OTHER ANALYSES

During the course of the study, the product administration form was updated to capture whether or not the subject remained in a recumbent position for 5 minutes after administration of study treatment. The primary efficacy analysis will be repeated as an exploratory, supplementary analysis of the primary outcome in **Table 55.** This analysis will be performed in the PP population, with the additional stipulation that the subject remain in the recumbent position for 5 of 6 doses to be considered compliant with study product. The number of subjects, the proportion of subjects who achieved clinical cure, and the 95% Wilson confidence interval for the proportion of subjects achieving clinical cure will be presented for each analysis population and treatment group. In addition, the difference in proportions between the 5% Monolaurin Vaginal Gel arm and the Placebo gel arm and 95% Wilson confidence intervals will be presented. A listing of subjects' product administration position for each dose is provided in **Listing 21**.

11. **REPORTING CONVENTIONS**

P-values ≥ 0.001 and ≤ 0.999 will be reported to 3 decimal places; p-values less than 0.001 will be reported as "<0.001"; p-values greater than 0.999 will be reported as "> 0.999". The mean, median, standard deviation, and any other statistics other than quantiles, will be reported to one decimal place greater than the original data. Quantiles other than the median will use the same number of decimal places as the original data. Proportions will be presented as two decimal
places; values <0.01 will be presented as "<0.01". Percentages will be reported to the nearest whole number; values < 1% will be presented as "<1". Estimated parameters, not on the same scale as raw observations (e.g. regression coefficients) will be reported to 3 significant figures.

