5% Monolaurin Vaginal Gel (N=X)							
			Number o	of Doses Administer	red n (%)		
	0	1	2	3	4	5	6
Product Administration Position	(N=X)	(N=X)	(N=X)	(N=X)	(N=X)	(N=X)	(N=X)
Recumbent	x (x)	x (x)	x (x)	x (x)	x (x)	x (x)	x (x)
Not Recumbent	x (x)	x (x)	x (x)	x (x)	x (x)	x (x)	x (x)
Placebo Gel (N=X)						•	
			Number o	of Doses Administer	red n (%)		
	0	1	2	3	4	5	6
Product Administration Position	(N=X)	(N=X)	(N=X)	(N=X)	(N=X)	(N=X)	(N=X)
Recumbent	x (x)	x (x)	x (x)	x (x)	x (x)	x (x)	x (x)
Not Recumbent	x (x)	x (x)	x (x)	x (x)	x (x)	x (x)	x (x)
All Subjects (N=X)		·	·	·	·		·
			Number o	of Doses Administer	red n (%)		
	0	1	2	3	4	5	6
Product Administration Position	(N=X)	(N=X)	(N=X)	(N=X)	(N=X)	(N=X)	(N=X)
Recumbent	x (x)	x (x)	x (x)	x (x)	x (x)	x (x)	x (x)
Not Recumbent	x (x)	x (x)	x (x)	x (x)	x (x)	x (x)	x (x)

Table 27: Product Administration Position and Number of Doses Administered - Safety Population

Note: Denominator for percentages is the number of subjects in the Safety Population for each Treatment Group who received the specified number of doses.

Site	Product Administration Position	Dose 1 n (%)	Dose 2 n (%)	Dose 3 n (%)	Dose 4 n (%)	Dose 5 n (%)	Dose 6 n (%)
	Recumbent	x (x)					
5% Monolaurin Vaginal Gel (N=X)	Not Recumbent	x (x)					
	Missing	x (x)					
	Recumbent	x (x)					
Placebo Gel (N=X)	Not Recumbent	x (x)					
	Missing	x (x)					
All Subjects (N=X)	Recumbent	x (x)					
	Not Recumbent	x (x)					
	Missing	x (x)					

Table 28: Product Administration Position by Treatment Group and Dose Number - Safety Population

Note: Denominator for percentages is the number of subjects in the Safety Population for each Treatment Group

Section 14.2 Efficacy Data

Table 29: Clinical Cure Results at the Test of Cure Visit, Visit 2 by Analysis Population and Treatment Group

Analysis Population	Treatment Group	Number of Subjects with Clinical Cure n	Number of Subjects N	Proportion of Subjects with Clinical Cure	Proportion of Subjects with Clinical Cure 95% CI	Difference in Proportion of Subjects with Clinical Cure between 5% Monolaurin Vaginal Gel and Placebo Gel	Difference in Proportion of Subjects with Clinical Cure between 5% Monolaurin Vaginal Gel and Placebo Gel 95% CI	P-Value*
	5% Monolaurin Vaginal Gel	Х	х	0.xx	0.xx, 0.xx	0.xx	0.xx, 0.xx	0.xxx
ITT	Placebo Gel	Х	х	0.xx	0.xx, 0.xx			
	All Subjects	Х	х	0.xx	0.xx, 0.xx			
	5% Monolaurin Vaginal Gel	Х	х	0.xx	0.xx, 0.xx	0.xx	0.xx, 0.xx	0.xxx
mITT	Placebo Gel	Х	х	0.xx	0.xx, 0.xx			

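### Tables 25 and 27 count women with no recorded administration position as Not Recumbent, although the form began asking about position only part-way through the study

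*SAP*

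**What the plan says.** SAP 10 states: "During the course of the study, the product administration form was updated to capture whether or not the subject remained in a recumbent position". It gives no date for the change and no count of women dosed before it. The list of changes in SAP 12 does not mention it.

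SAP 9.2 gives the rules for Tables 25 (by site) and 27 (by treatment group). A woman counts as Recumbent "if they administer each of the specified number of doses in the recumbent position". A woman who "is missing product administration position, they will appear in the" Not Recumbent rows. The shells have only these two rows. Their denominators are all Safety Population subjects in that site or treatment group who received the stated number of doses.

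For Tables 26 and 28, SAP 9.2 handles the same gap differently: a subject who "did not enter the position they were in for the dose" forms a separate category, and the shells carry a Missing row. Listing 21 also shows Missing, dose by dose.

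SAP 10 then repeats the primary efficacy analysis in Table 55 among PP women and adds a requirement: "with the additional stipulation that the subject remain in the recumbent position for 5 of 6 doses to be considered compliant with study product". It gives no rule for missing position and describes the analysis as exploratory and supplementary.

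**The concern.** Under the SAP 9.2 rule, a question that was not asked is recorded as a negative answer. A clinical study report reader would take the Not Recumbent row of Table 27 as the share of women who did not stay recumbent. Part of that row may be women about whom nothing is known. The rule also reaches past the early enrollees. Recumbent requires every administered dose, so a single blank entry after the form change moves a woman into the wrong row.

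Table 25 has a further exposure because it is split by site. SAP 12 records that one site joined later, under protocol version 6.0. If the share never asked differs between sites, the table can show a difference in administration that reflects only which form was in use.

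Table 55 raises a related but smaller question. A woman never asked cannot be shown to meet the recumbency condition. As worded, that condition makes her non-compliant rather than not assessed.

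**Working it through.** **Plan's own figure.** The plan gives no figure on this point, so there is none to reproduce.

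**Inputs from the documents**
- Missing position goes to Not Recumbent in Tables 25 and 27 (SAP 9.2).
- The denominator is every Safety Population subject with that number of doses (shells of Tables 25 and 27).
- Position was collected only after a mid-study form change (SAP 10).

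**Inputs that must be assumed**
- r: the true share of women recumbent at every administered dose.
- f: the share of women with no recorded position.
- r is taken to be the same in women with and without a record.

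**Formulas**
- Recumbent share shown under SAP 9.2: r(1 − f).
- Not Recumbent share shown: 1 − r(1 − f).
- True Not Recumbent share: 1 − r.
- Overstatement: [1 − r(1 − f)] − (1 − r) = rf.

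**Not Recumbent share shown**

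| Assumed r | True share | f = 0.10 | f = 0.25 | f = 0.50 | f = 0.75 |
|---|---|---|---|---|---|
| 0.70 | 30% | 37% | 47.5% | 65% | 82.5% |
| 0.90 | 10% | 19% | 32.5% | 55% | 77.5% |
| 1.00 | 0% | 10% | 25% | 50% | 75% |

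For r = 0.90 and f = 0.25: 1 − 0.90 × 0.75 = 0.325. If the denominator is limited to women with recorded position, the result is 1 − r whatever f is.

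**Site comparison (Table 25).** Take r = 0.90 at two sites, with f = 0 at one and f = 0.50 at the other. Not Recumbent shows as 10% and 55%, although behaviour is identical. The documents do not say whether the form change came before or after the late site opened, so this shows only what can happen.

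**Table 55.** Here women are lost rather than relabelled. Start from an optimistic 60 and 30 PP women by arm, and assume 90% of those asked meet the condition. The numbers left are 60 × 0.90 × (1 − f) and 30 × 0.90 × (1 − f):
- f = 0: 54 and 27.
- f = 0.25: about 40 and 20.
- f = 0.50: about 27 and 14.

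Exact power of Fisher's test for cure rates of 0.50 against 0.20 would be 0.71, 0.57 and 0.41. The same calculation at 60 and 30 gives 0.783, against .78 in the SAP 5 table. The Table 55 shell carries no p-value, so these powers only indicate the loss of precision.

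**The case against.** The rule is stated openly, and the missing data are not hidden: Tables 26 and 28 and Listing 21 show them separately, and Tables 19 and 20 give first-treatment dates by site and arm. Tables 25 and 27 count subjects while Tables 26 and 28 count by dose, so the two pairs would differ in any case. No primary, secondary or safety endpoint uses position. All of this is correct. It limits the importance of the point, but it does not make the Not Recumbent row right, and it shows that the SAP already has the category it leaves out here.

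A reader might infer more than the documents support:

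- *That every woman dosed before the change is misclassified.* Some may truly not have been recumbent. They are classified without data, which is a different statement.
- *That Table 55 also misstates how the gel was used, or compares late enrollees with the whole PP set.* Its shell compares the two arms among PP women documented as recumbent. Randomization is in permuted blocks stratified by site (SAP 4.4.2), so losses due to the form date should fall roughly evenly on both arms. Calendar time, the added site and the eligibility changes matter only if someone sets Table 55 beside the PP row of Table 29.
- *That the Table 55 wording excludes a woman recumbent for all six doses.* The phrase "remain in the recumbent position for 5 of 6 doses to be considered compliant with study product" modifies a compliance rule that SAP 3.3.9 and 9.2 both set at five or more of six. The wording should match, but the exclusion is not a realistic reading.
- *That women were given no instruction on position.* Protocol 6.2 refers to verbal and written instructions whose content is not in the documents.

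**Conclusion.** The point holds for Tables 25 and 27. As written, they report women with no recorded position as Not Recumbent and overstate that share by rf. The size cannot be fixed from the documents, because they give neither the date of the form change nor the number of women before it. At an assumed r = 0.90, the overstatement is 9 percentage points at f = 0.10, 22.5 at f = 0.25 and 45 at f = 0.50. The conclusion assumes that position was not recovered retrospectively, which the documents do not mention.

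For Table 55 the finding is narrower. The SAP does not say how missing position is handled, and the loss of earlier women is an inference from the condition. The likely costs are precision and generalizability rather than a biased comparison of the arms. The affected outputs are descriptive or exploratory, and the primary mITT analysis does not change.

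**What to change.** 1. **Tables 25 and 27.** Add a Missing / not collected row, and base the Recumbent and Not Recumbent percentages on women with recorded position. Replace the SAP 9.2 sentence that sends missing position to Not Recumbent.
2. **Table 55.** State that women with no recorded position are excluded as not assessed, not as non-compliant. Word the condition as at least 5 of 6 doses.
3. **Table 55 footnote.** Give the date of the form change and the number of PP women dosed before it, so that the table is not read against the full PP result as evidence about position.

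The cost is a few sentences in SAP 9.2 and 10, one extra row in two shells, and one footnote. No new data are collected. Restricting Table 55 to women dosed after the change would add little, because that is essentially the set it already yields.
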